## 1 Introduction to RAP documentation

### 1.1 Scope

The RAP documents contain detailed information to aid the production of Statistics & Programming input into the Clinical Study Report (CSR) for trial “CVAY736X2203”.

**Module 3 (M3)** provides the description of the statistical methodology used to analyze the data, **Module 7 (M7)** details the presentation of the data, including shells of summary tables, figures and listings, and **Module 8 (M8)** contains programming specifications e.g. for derived variables and derived datasets, to support the creation of CSR outputs.

### 1.2 Changes to RAP documentation (M3)

Commercially Confidential Information

**For the statistical methodology (M3)**, any major changes occurring before database lock to the statistical methodology should be reflected in the RAP M3 documentation via version control (new document version to be approved by the trial team as the original module).

Major changes include, but are not limited to, changes in protocol that affect study design and statistical methodology.

Minor changes to the RAP M3 documentation can be captured e.g. by a study note to file / note in RAP Addendum or within the CSR itself. Minor changes include, but are not limited to, change in statistical model. Corrections of typographical errors or modification of spelling (from English to American, for example) do not need to be incorporated into the RAP M3 documentation.

## **2 Study objectives and design**

### **2.1 Study objectives**

#### **2.1.1 Primary Objective**

- To compare the efficacy of single i.v. doses of VAY736 relative to placebo in reducing clinical disease activity of pemphigus vulgaris patients, as determined by the change in Pemphigus Disease Area Index (PDAI) between baseline and 12 weeks

#### **2.1.2 Secondary objective(s)**

- To evaluate the safety and tolerability of VAY736 in patients with PV
- To evaluate the effect of VAY736 in PV patients as assessed by the Autoimmune Bullous Skin disease Intensity Score (ABSIS) at 12 weeks
- To evaluate the effect of VAY736 in PV patients as assessed by Investigator Global Assessment (IGA) at 12 weeks
- To evaluate VAY736 pharmacokinetics in serum in PV patients

#### **2.1.3 Exploratory objective(s)**

Commercially Confidential Information

## 2.2 Study design and treatment

This is a non-confirmatory, randomized, partial-blind, placebo-controlled trial evaluating the efficacy, safety, pharmacokinetics and pharmacodynamics of VAY736 in the treatment of patients with pemphigus vulgaris.

Up to approximately 32 patients will be randomly assigned in a blinded fashion to one of three single dose treatment arms, and at least 24 patients are expected to complete the study. Recruitment will be staggered and progression between doses is dependent upon a safety review milestone (see [Figure 2-1](#)).

[figure not shown]
In the pre-safety review period, 9 patients will be randomized to a single dose of either 3 mg/kg VAY736 or placebo (6 dosed with VAY736 and 3 with placebo). After dosing of these 9 initial patients, recruitment will be paused and a safety review will be conducted by an internal Data Monitoring Committee (DMC), independent from the VAY736 project team.

The DMC will review all safety data available to the 9th patient achieving Week 6. If there are no safety signals identified by this safety review, recruitment will restart into the 3 mg/kg VAY736 and placebo treatment arms, and will commence to the 10 mg/kg VAY736 treatment arm. If there is a safety signal enrollment will be put on hold, pending a full data evaluation.

Following treatment on Day 1 with study medication, standard of care (SoC) medications are to be maintained at a stable dose level with minimal dose adjustments until “disease control” in signs/symptoms of PV. “Disease control” is defined as the time at which new lesions cease to form and established lesions begin to heal. A protocol-defined SoC medication taper begins once a patient reaches disease control, to safely deliver the patient to the lowest dose needed to maintain control of their disease.

[figure not shown]
At study completion, it is intended that 9 patients will have been dosed with VAY736 at 3 mg/kg, 9 patients with 10 mg/kg, and 6 patients with placebo.

**Figure 2-1 Study design: Staggered recruitment**

The study will consist of the following Phases (see [Figure 2-2](#)):

Figure 2-2 Study design: Visit Schedule

Key: B: Baseline; R: Randomization; U: unblinding of patient treatment; \*: Placebo patients may enter into open-label VAY736 treatment and restart the study at Day 1; Commercially Confidential Information

### 3 First interpretable results (FIR)

Commercially Confidential Information

### 4 Interim analyses

Commercially Confidential Information

Commercially Confidential Information

## **5 Statistical methods: Analysis sets**

For subjects for which the actual treatment received does not match the randomized treatment the treatment actually received will be used for the analysis.

All subjects that received study drug and with no protocol deviations with relevant impact on safety will be included in the safety analysis set.

The PK analysis set will include all subjects with at least one available valid (i.e. not flagged for exclusion) PK concentration measurement, who received any study drug and experienced no protocol deviations with relevant impact on PK data.

Commercially Confidential Information

The analysis sets and protocol deviation codes are related as follows:

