1.2 Study purpose

The purpose of the study is to determine if single i.v. doses of VAY736 can reduce disease activity in PV, determined by the change in Pemphigus Disease Area Index (PDAI) as compared to placebo. The study will also provide the first safety and tolerability information for VAY736 in PV patients.

2 Study objectives

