9.1 Analysis sets

For all analysis sets, subjects will be analyzed according to the study treatment(s) received.

The full analysis set will include all subjects that received any study drug.

The safety analysis set will include all subjects that received any study drug.

The PK analysis set will include all subjects with available PK data and no protocol deviations with relevant impact on PK data.

The primary PK analysis set will include all subjects with available PK data. The secondary PK analysis set will include all subjects with available PK data and no protocol deviations with relevant impact on PK data.

Commercially Confidential Information

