9.5.2 Safety

Vital signs

All vital signs data will be listed by treatment, subject, and visit/time and if ranges are available abnormalities (and relevant orthostatic changes) will be flagged. Summary statistics will be provided by treatment and visit/time.

ECG evaluations

All ECG data will be listed by treatment, subject and visit/time, abnormalities will be flagged. Summary statistics will be provided by treatment and visit/time.

Clinical laboratory evaluations

All laboratory data will be listed by treatment, subject, and visit/time and if normal ranges are available abnormalities will be flagged. Summary statistics will be provided by treatment and visit/time.

Adverse events

All information obtained on adverse events will be displayed by treatment and subject.

The number and percentage of subjects with adverse events will be tabulated by body system and preferred term with a breakdown by treatment. A subject with multiple adverse events within a body system is only counted once towards the total of this body system.

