**Table 5-1 Protocol deviation severity codes and analysis sets**

Protocol deviation severity code		Safety analysis set	PK analysis set	
Code	Text			
5	Exclude subject from all safety analysis	-	-	Commercially Confidential Information
8	Exclude from all analyses	-	-	
20	Exclude subject from PK analysis set	+	-	
Commercially Confidential Information				
49	Report relevant protocol deviation – include subject in all analysis sets	+	+	

+ = include in analysis set, - = exclude from analysis set, NA = not applicable

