### Adverse events

The number and percentage of subjects with adverse events will be tabulated by treatment, system organ class, and preferred term. Additionally the summary table with a breakdown by the severity of adverse events will also be provided. An adverse event starting at one time-point and continuing to another time-point will be counted only at the onset time-point. A

subject with multiple adverse events within a system organ class is only counted once towards the total of this system organ class.

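### The SAP drops dosed patients from the safety set for certain protocol deviations; the protocol keeps everyone who was dosed

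*SAP*

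**What the plan says.** Protocol 9.1 defines the set by exposure alone: "The safety analysis set will include all subjects that received any study drug". In the legible text of that section, only the PK sets carry a condition about deviations.

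SAP section 5 adds a second condition: "All subjects that received study drug and with no protocol deviations with relevant impact on safety will be included in the safety analysis set". Table 5-1 then links deviation codes to analysis sets:

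- Code 5, "Exclude subject from all safety analysis": minus for safety, minus for PK.
- Code 8, "Exclude from all analyses": minus for safety, minus for PK.
- Code 20, exclusion from the PK set: plus for safety, minus for PK.
- Code 49, a reportable deviation with the instruction "include subject in all analysis sets": plus for both.

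The table's legend defines minus as exclusion.

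On reporting, Protocol 9.5.2 says: "All information obtained on adverse events will be displayed by treatment and subject". The adverse event paragraph in SAP section 9 mentions only counts and percentages: "The number and percentage of subjects with adverse events will be tabulated by treatment, system organ class, and preferred term".

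**The concern.** A safety set normally contains everyone exposed, so that no harm seen under treatment can drop out of the tables. Here the SAP removes dosed patients, and the criterion is the deviation's bearing on safety. The patients whose adverse events may be most informative are therefore the ones who can be left out. The legible text gives no rule for judging that bearing and does not say who assigns the codes. Protocol 8.3 settles deviations before the database is locked. By then, however, patients will have been unblinded individually at Week 24 or earlier (Protocol 5.5.8), and Table 16-1 then allows the statistician and the clinical trial leader, among others, to know individual assignments. Blinding therefore gives only limited protection against selective coding.

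Safety and tolerability is a secondary objective (Protocol 2.2), and Protocol 1.2 says: "The study will also provide the first safety and tolerability information for VAY736 in PV patients". A summary that omits some exposed patients would weaken that evidence. If code 5 or 8 is given to any dosed patient, the study report must also depart from either the protocol or the SAP.

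**Working it through.** There is no stated figure to reproduce. The check compares the texts and then illustrates the effect.

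**1. Do the definitions differ?**

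| Dosed subject with | Protocol 9.1 | SAP section 5 and Table 5-1 |
|---|---|---|
| no coded deviation | in | in |
| code 20 or 49 | in | in |
| code 5 or 8 | in | out |

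The last row is the contradiction. It stands in the current text of both documents.

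**2. Is it a permitted refinement?** Protocol 9.4.2 refers alternative methods for the primary variable to the analysis plan. The legible text of Protocol 9.1 gives no such latitude for the safety set, and Protocol 11.1 requires a written amendment for any change to the protocol.

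**3. How much could one exclusion matter?** Inputs: intended dosed numbers of 9 (3 mg/kg), 9 (10 mg/kg) and 6 (placebo), from Protocol 3.1 and SAP 2.2. The single exclusion and the event counts are assumptions.

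Weight of one patient: 1/9 = 11.1%; 1/6 = 16.7%; 1/18 = 5.6% of both VAY736 arms together.

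| True count | Excluded patient had the event | Excluded patient did not |
|---|---|---|
| 1/9 = 11.1% | 0/8 = 0% | 1/8 = 12.5% |
| 2/9 = 22.2% | 1/8 = 12.5% | 2/8 = 25.0% |
| 1/6 = 16.7% | 0/5 = 0% | 1/5 = 20.0% |

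For an assumed 2/9 on one dose and 1/6 on placebo, the difference is 22.2% − 16.7% = +5.6 points from unrounded fractions. After one exclusion it is one of:

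- VAY736 patient with the event: 1/8 − 1/6 = −4.2 points
- VAY736 patient without it: 2/8 − 1/6 = +8.3 points
- placebo patient with the event: 2/9 − 0/5 = +22.2 points
- placebo patient without it: 2/9 − 1/5 = +2.2 points

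When no event of a type is seen, the exact one-sided 95% upper bound is 1 − 0.05^(1/n). It rises from 28.3% (n = 9) to 31.2% (n = 8), and from 39.3% (n = 6) to 45.1% (n = 5).

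**4. Sensitivity to enrolment.** Up to about 32 patients may be randomized. At 32 in the overall 3:3:2 ratio (Protocol 5.2) the arms are 32 × 3/8 = 12, 12 and 32 × 2/8 = 8. One patient is then 1/12 = 8.3% or 1/8 = 12.5%, which is smaller but still visible.

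**The case against.** The best case on the other side concerns weight rather than fact.

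- **The trial is non-confirmatory, safety is reported descriptively, and perhaps nobody would receive code 5 or 8.** All true. This limits the expected consequence but does not remove the contradiction.
- **An excluded patient would probably still be traceable.** SAP section 9 lists all vital signs, ECG and laboratory data and shows the disposition of everyone randomized, and Protocol 11 requires significant deviations to appear in the study report. This stands in part. None of it puts the patient back into the summary percentages, and the wording of code 5 could be read to cover listings too. The shells for adverse event listings are in a separate module that is not available, so it is unclear whether those listings also lose the patient.
- **A reason may lie under the redactions.** Parts of SAP 1.2, section 5 and Table 5-1 are blacked out, so the absence of a visible reason proves little. The rule itself is fully legible.
- **Code 8 may be meant for subjects never dosed, or for data that may not be used at all.** The documents do not say. This is a fair caution, and the fix allows for it. It does not apply to the SAP sentence, which imposes the condition on subjects who received study drug.
- **Patients given prohibited treatment are not shown to receive these codes.** Correct. Protocol 5.5.10 has some of them followed for safety, so it would be odd to collect their data and then drop them, but that link is only a possibility.
- **The between-arm difference is computed for assumed counts, and no such comparison of adverse events is visibly planned.** Also correct. It shows only how sensitive small arms are.

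**Conclusion.** The concern holds. The SAP's safety set is narrower than the protocol's, and following the SAP as written removes any dosed patient with code 5 or 8 from the safety summaries. This should be corrected before database lock. The conclusion rests on the legible text alone. The size and direction of any bias are unknown, because neither the coding rules nor the number of affected patients is given. Under the assumption of one exclusion at the intended arm sizes, an event can vanish from an arm's table, and even the sign of a small difference between arms can change. The effect is confined to the safety summaries in the study report. Expedited reporting of serious events (Protocol 7.2) and committee review (Protocol 8.4) do not use this set, and the primary efficacy comparison is not shown to be affected.

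**What to change.** - **SAP section 5:** define the safety set as every subject given any amount of study drug, analysed by the treatment actually received, whatever deviations are recorded.
- **Table 5-1, code 5:** delete it. A subject who must leave only the PK set takes code 20; where no set is affected, code 49 applies.
- **Table 5-1, code 8:** limit it to non-safety analyses, with a plus in the safety column for dosed subjects. If it is meant for data that may not be used at all, state that reason and report each such dosed subject separately.
- **Reporting:** list the deviations of the subjects concerned, and show any safety summary without them only as a labelled sensitivity analysis.

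The cost is a few lines of SAP text, two table rows and one deviation listing. No sample size or other design figure changes. At the intended arm sizes the safety denominators become 9, 9 and 6, or 24 in all.

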**Table 5-1 Protocol deviation severity codes and analysis sets**

Protocol deviation severity code		Safety analysis set	PK analysis set	
Code	Text			
5	Exclude subject from all safety analysis	-	-	Commercially Confidential Information
8	Exclude from all analyses	-	-	
20	Exclude subject from PK analysis set	+	-	
Commercially Confidential Information				
49	Report relevant protocol deviation – include subject in all analysis sets	+	+	

+ = include in analysis set, - = exclude from analysis set, NA = not applicable

## 6 Statistical methods for Pharmacokinetic (PK) parameters

Commercially Confidential Information

Pharmacokinetic parameters will be listed by treatment and subject. Descriptive summary statistics will include mean (arithmetic and geometric), SD, and CV (arithmetic and geometric), median, minimum and maximum. An exception to this is Tmax where median, minimum and maximum will be presented.

## 7 Statistical methods for Pharmacodynamic (PD) parameters

Commercially Confidential Information

### 7.1 Analysis of the primary variable(s)

The primary aim of this study is to compare the efficacy of a single i.v. dose of VAY736 in reducing the clinical disease activity of pemphigus vulgaris patients as determined by the change in Pemphigus Disease Area Index (PDAI) between baseline and week 12.

#### 7.1.1 Variable(s)

The primary efficacy variable is the total skin and mucous membranes activity score (PDAI score). The score is weighted for the number and size of lesions with a score of 0 (absent) to 10 given for skin (12 body locations), scalp and mucous membrane showing disease activity (erosions/blisters or new erythema). To be more precise at the lower end of the PDAI score the value of 1 that included 1-3 lesions on each anatomic region is split in intervals: 1

corresponds to one lesion (none greater than 2 cm); 1.3 corresponds to two lesions and 1.6 corresponds to three lesions.

Damage, such as post inflammatory hyperpigmentation or erythema from resolving lesion, is scored separately from the main score as absent (0) or present (1) for each body area or scalp resulting in a score of 0 to 12 or 0 to 1, respectively. Therefore the PDAI score ranges from 0 to 263, with 250 points representing disease activity (120 points for skin activity; 10 points for scalp activity; 120 points for mucosal activity) and 13 points representing disease damage.

### **7.1.2 Statistical model, hypothesis, and method of analysis**

It is assumed that the PDAI skin and mucous membranes activity score will follow an approximate normal distribution.

Individual profile figures of PDAI and Mean (SD) plots by time and treatment will be produced for absolute and changes from baseline (including percentage changes from baseline). Similar Mean (SD) plots will be produced for the PDAI subscores: as detailed in [Section 7.1.1](#). Summary statistics of absolute and changes from baseline (including percentage changes from baseline) by time and treatment will be presented.

Scatterplots of PDAI at 12 weeks versus total SoC use and also versus selected biomarkers will be presented.

### **7.1.3 Handling of missing values/censoring/discontinuations**

Patients with missing PDAI at baseline will not be included in the analysis. Patients with missing data at one or more timepoints post baseline will be included in the analysis.

### **7.1.4 Supportive analyses**

Not applicable.

## **7.2 Analysis of secondary** Commercially Confidential Information

Secondary efficacy variables supporting the secondary objectives are:

- PDAI total score recorded at baseline and weeks 3, 6, 9, 12, 16, 20 and 24.
- ABSIS recorded at baseline and weeks 3, 6, 9, 12, 16, 20 and 24.
- IGA recorded at baseline and weeks 3, 6, 9, 12, 16, 20 and 24.

Commercially Confidential Information

Commercially Confidential Information

### 7.2.1 Variables

Autoimmune Bullous Skin disorder Intensity Score (ABSIS) is a quality- and quantity-based score for cutaneous and oral mucosal lesions combining the extent of the affected body surface area (BSA), the quality of the skin lesions and oral involvement, the ABSIS score ranges from 0 to 206 with 150 points for skin involvement, 11 points for oral involvement and 45 points for subjective discomfort during eating and drinking.

Investigator global assessment score (IGA) is a score on a 0-4 scale to assess each patient's PV disease activity.

Commercially Confidential Information

### 7.2.2 Efficacy / Pharmacodynamics

The secondary Commercially Confidential Information efficacy variables will be analysed as follows:

The PDAI total score, ABSIS score will be analyzed following the same approach used for the primary efficacy variable.

Commercially Confidential Information

## 8

### Commercially Confidential Information

## 9 Statistical methods for safety and tolerability data

Open label VAY736 and the placebo data from before the patients were transferred to open label VAY736 will be presented as separate treatments in the outputs.

All data for background and demographic variables will be listed by treatment group and subject. Summary statistics will be provided by treatment group.

Subject disposition will be listed and summarized by treatment. In addition a figure displaying the subject disposition of all randomized subjects will be produced.

The number of subjects assessed by visit will be summarized in a frequency table and presented in a heatmap.

Relevant medical history, current medical conditions, results of laboratory screens, drug tests and any other relevant information will be listed by treatment group and subject. Data for study drug administration and concomitant therapies will be listed by treatment group and subject.

Boxplots to visualize trends in longitudinal safety data (vitals, ECG, lab parameter) will be created.

### Adverse events

The number and percentage of subjects with adverse events will be tabulated by treatment, system organ class, and preferred term. Additionally the summary table with a breakdown by the severity of adverse events will also be provided. An adverse event starting at one time-point and continuing to another time-point will be counted only at the onset time-point. A

subject with multiple adverse events within a system organ class is only counted once towards the total of this system organ class.

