After 24 weeks in the study, at the Week 24 visit (or before in case of early withdrawal from the double-blind period that meets certain conditions – see [Section 5.5.8](#)), patients' treatment will be unblinded. When the blind is broken and a patient was assigned to placebo during the double blind period, such a patient will be offered the option to receive open label VAY736 administration from approximately one week after the Week 24 visit, and will follow the same visit pattern as if re-starting from Day 1. Patients will be assigned a new patient number for the open-label treatment. Patients joining the open label part of the study have to satisfy inclusion for active disease and safety labs as mentioned in [Section 4](#), within 2 weeks of their prior Week 24 visit. The dose of VAY736 administered will be 3 mg/kg if a patient reaches Week 24 prior

to the study safety review or 10 mg/kg if dosed after a favorable safety review by the DMC. If a patient prefers not to receive open label active treatment, they are to return within 4 weeks for their EoS visit.

For logistical reasons, it may be necessary for patients to come to the site or a hotel the evening before their scheduled assessment visit, or remain at the site following the visit (e.g. transport restrictions, long travel times from home to site). In these instances, the patients would be hospitalized at the site, but this would not be considered as an SAE.

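### The by-treatment adverse event table has no stated common onset window, although VAY736 patients can be followed for ordinary adverse events about twice as long as placebo patients

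*SAP*

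**What the plan says.** SAP section 9, Adverse events: "The number and percentage of subjects with adverse events will be tabulated by treatment, system organ class, and preferred term". A severity breakdown is added, and a subject counts once per system organ class. One timing rule is given: "An adverse event starting at one time-point and continuing to another time-point will be counted only at the onset time-point". The time-points are not defined there.

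Protocol 9.5.2 plans the same table, "The number and percentage of subjects with adverse events will be tabulated by body system and preferred term with a breakdown by treatment", together with a subject-level display: "All information obtained on adverse events will be displayed by treatment and subject".

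SAP section 9 fixes the end of the placebo column for patients who switch: "Open label VAY736 and the placebo data from before the patients were transferred to open label VAY736 will be presented as separate treatments". It also plans a view of follow-up: "The number of subjects assessed by visit will be summarized in a frequency table and presented in a heatmap".

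The length of follow-up is set in the protocol:

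- **Placebo.** Section 3.1 unblinds at Week 24 and offers open-label VAY736 about one week later. For the others: "If a patient prefers not to receive open label active treatment, they are to return within 4 weeks for their EoS visit". Section 5.5.8 allows unblinding at Week 12 or later after a second increase in standard of care.
- **VAY736.** The synopsis and section 5.5.8 move these patients into long-term follow-up. Section 5.5.11 lists visits up to Week 100.
- **Collection.** Section 7.1 has all adverse events reported to Week 52 and, from Week 76, only selected non-serious ones (related events, infections, potential malignancies, neutropenia). Section 7.2 keeps serious events reportable until 30 days after End of Study.

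**The concern.** A crude percentage of subjects with an event rises with observation time whenever events keep accruing. If one column stops near Week 25 to 28 and the others can run to Week 52, identical drugs would show different percentages.

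Safety and tolerability is the first secondary objective, and protocol 3.4 gives objective evidence on adverse events as a reason for having a placebo arm. The extra VAY736 time also covers risks that the protocol itself raises in sections 3.6.1 and 3.6.2, namely infection and late-onset neutropenia, in a period with little or no placebo time. Events after Week 24 are moreover reported by investigators who know the treatment, whereas most placebo data are blinded. One unwindowed VAY736 column would mix both kinds of report.

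**Working it through.** The plan states no adverse event rate and no exposure figure, so there is nothing of its own to reproduce. The check has two steps.

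**Step 1. Time at risk for ordinary adverse events**

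- Placebo, open label accepted: 24 + 1 = Week 25 (protocol 3.1; SAP section 9 ends the column there).
- Placebo, open label declined: by 24 + 4 = Week 28 (protocol 3.1).
- VAY736: Week 52 at most (protocol 7.1). The actual length follows the Appendix 5 decision tree, which is not shown, and can be shorter.
- Ratio: 52/28 = 1.86 to 52/25 = 2.08.

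**Step 2. Effect on a crude percentage when the drug does nothing**

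Assumptions: 20% of placebo patients have the event by the placebo end t0 (25 or 28 weeks), and the hazard is the same in all arms.

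- Constant hazard: risk at week w = 1 − 0.80^(w/t0).
- Falling hazard (Weibull, shape 0.5): risk at week w = 1 − 0.80^((w/t0)^0.5).

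| VAY736 followed to | Constant, t0 = 25 | Constant, t0 = 28 | Falling, t0 = 25 | Falling, t0 = 28 |
|---|---|---|---|---|
| Week 32 | 24.8% | 22.5% | 22.3% | 21.2% |
| Week 40 | 30.0% | 27.3% | 24.6% | 23.4% |
| Week 52 | 37.1% | 33.9% | 27.5% | 26.2% |

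From a Week 24 base, the falling hazard gives 1 − 0.80^((52/24)^0.5) = 28.0% at Week 52.

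In patients, with the planned 9, 9 and 6 (protocol 3.1), placebo expects 6 × 0.20 = 1.2. A matched VAY736 arm expects 9 × 0.20 = 1.8. A VAY736 arm followed to Week 52 expects 9 × 0.339 = 3.1 to 9 × 0.371 = 3.3 (constant hazard), or 9 × 0.262 = 2.4 to 9 × 0.275 = 2.5 (falling hazard).

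With other assumed placebo risks and a constant hazard, 10% becomes 17.8% to 19.7% at Week 52, and 30% becomes 48.4% to 52.4%. Events confined to the infusion day occur in all arms before follow-up diverges, so their bias is close to nil.

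**Sensitivity to longer placebo follow-up.** Protocol Table 5-3 and section 5.5.11 do not limit follow-up after withdrawal by arm. If 1 of 6 placebo patients also reached Week 52, placebo would show (5 × 0.20 + 0.371)/6 = 22.9% (t0 = 25) or (5 × 0.20 + 0.339)/6 = 22.3% (t0 = 28). With 2 of 6 the figures are 25.7% and 24.6%. The gap to a VAY736 arm followed to Week 52 under the same constant hazard narrows but does not close.

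**The case against.** The strongest reply is that the window may be set in text that is not visible. SAP 1.1 assigns table layout to Module 7, which "details the presentation of the data, including shells of summary tables, figures and listings", and derived variables to Module 8; neither is available. SAP sections 3 and 4 are redacted, and protocol 5.4 mentions an interim analysis after all patients have passed Week 24, so a Week 24 cut may exist. The onset time-point rule also makes most sense if events are tabulated by period. This stands as a limit: a reader might infer that the trial has no window anywhere, and the documents do not support that. But SAP 1.1 gives methodology to Module 3, an onset window decides which events count, and the adverse event text of that module shows no redaction. The rule on onset time-points prevents double counting but names no periods.

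A second reply is that follow-up lengths are less certain than they look. Placebo patients can be ineligible for open label (protocol 4.1 and 4.2), and their path is not visible. The length of VAY736 follow-up is partly redacted. This also stands, so the ratio is an upper range for planned time, not a figure for every patient.

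A third is that the trial is small and non-confirmatory, the table is descriptive, and the subject-level display and heatmap let a reader match periods by hand. That limits the harm but leaves the summary percentages unmatched.

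**Conclusion.** The point holds. Followed as written, the by-treatment table compares crude percentages over unequal periods. For ordinary adverse events the planned time can be up to about 1.9 to 2.1 times longer on VAY736. With no drug effect and an assumed 20% placebo risk, that could turn 20% into about 34% to 37% under a constant hazard, or about 26% to 28% under a falling one, for an arm followed to Week 52. These figures rest on an assumed rate and on Week 52 as a maximum.

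Some stronger readings go too far:

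- A reader might infer a ratio near 4 from the Week 100 visit. Protocol 7.1 restricts non-serious events from Week 76 to selected types, and the decision tree can end follow-up earlier.
- A reader might take Week 24 as the placebo end and get 52/24 = 2.2. Placebo data run on to about Week 25 to 28, so that ratio is too high for patients who complete the blinded period.
- A reader might infer that serious events are collected only in certain periods. Protocol 7.2 has them reportable throughout, until 30 days after End of Study.
- A reader might infer that the table hides harm or invalidates a test. The bias overstates VAY736 risk and no test is planned on it; the harm is misreading.

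This should be fixed because the remedy is cheap and the comparison serves a secondary objective.

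**What to change.** State the following in SAP section 9:

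1. The between-arm table (3 mg/kg, 10 mg/kg, placebo) counts events with onset from Day 1 to the Week 24 visit (Day 169) in every arm, whether or not the patient was unblinded earlier. The window ends sooner only at transfer to open-label VAY736 or exit from the study. Patient-time per arm stands beside n (%).
2. Because those early ends may follow disease worsening and differ by arm, exposure-adjusted rates are added for overall events, serious events and infections. If 1 or 2 of 6 placebo patients transferred at Week 12, a 20% risk at 24 weeks (constant hazard) would show as 18.4% or 16.9%, since the 12-week risk is 1 − 0.80^0.5 = 10.6% and (5 × 0.20 + 0.106)/6 = 18.4%. Rates by preferred term are not useful: full placebo time is 6 × 168/365.25 = 2.76 patient-years, and one event gives 0.36 per year with an exact 95% interval of 0.009 to 2.02.
3. Later events go in a separate table with patient-years, marked as unblinded and, from Week 76, as selectively collected for non-serious events.
4. If Module 7, Module 8 or a redacted section already defines these periods, a cross-reference in SAP section 9 is enough.

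The cost is SAP wording, one extra table and a derived cut-off date. Start dates of adverse events are already recorded (protocol 7.1). No visit or treatment rule changes.
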